Referral pathway initiation. Within seven calendar days of AYA NA-SB completion, the implementation leader will review completed needs assessments and, depending on AYAs' preferences indicated at the end of the needs assessment, will either (a) initiate appropriate referral pathways, or (b) provide a list of recommended referrals to AYAs. For each needs assessment reviewed, they will document these actions on a brief fidelity checklist which timestamps their completion of these tasks, documents the referral pathways selected, and gauges their confidence in selecting appropriate referral pathways (**Appendix B**). This process is expected to take less than 10 minutes/ needs assessment.

Postintervention AYA survey. One month following their completion of the needs assessment, I will engage AYA pilot participants in an online postintervention survey (**Appendix C**) assessing their perceptions of AYA NA-SB's feasibility, acceptability, and appropriateness. In addition to items assessing AYAs' perspectives of the needs assessment itself, this survey will solicit information about the follow-up care AYAs received in response to needs they reported in the needs assessment and whether they felt their needs were met (Aim 2). This survey will administered through RedCAP and will take approximately 15 minutes to complete. AYAs will receive a second \$15 incentive for completing the postintervention survey.

Postintervention provider interview. I will conduct a semi-structured interview with the implementation leader and other participating providers from NCCH after AYA NA-SB has been administered to a minimum of n=15 AYAs. The purpose of this 1-hour interview is to assess provider perceptions of the feasibility, acceptability, and appropriateness of AYA NA-SB and to elicit information about perceived implementation determinants and strategies deployed. Interviews will be recorded and transcribed for analysis. **Appendix D** contains the interview guide.

Activity	Provider Training	Needs assessment administration	Referral pathway initiation	Postintervention AYA survey	Postintervention provider interview
Time	0	+6 weeks	+7 weeks	+10 weeks	+10-15 weeks

Instruments & procedure (Aims 3)

I will conduct annual semi-structured qualitative interviews with AYA providers and program leaders from diverse health systems to proactively address challenges and prepare for future AYA NA-SB scale-up and sustainability.

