An interview guide (**Appendix E**) was developed using domains and constructs from the Dynamic Sustainability Framework, which conceptualizes the dynamic relationship among interventions, practice settings, and broader systems over time. ¹⁹ During interviews, I will review pilot data with providers and ask them to consider how AYA NA-SB's implementation and outcomes might unfold similarly or differently in their health systems given their practice context (e.g., staffing, informational systems, culture) and broader context (e.g., policy, regulations, market forces).

I will conduct interviews via telephone at a time of participants' choosing. Interviews will last approximately 60 minutes. They will be recorded and transcribed for analysis.

Outcome Measure(s)

Variable	Definition	Measure	Participants	Data source				
Demographic/clinical variables (Aim 1, Aim 2)								
Demographics	Age; sex; race/ethnicity; healt	AYAs	Needs assessment					
Clinical	Cancer diagnosis; stage at dia	AYAs	Needs Assessment					
variables		_						
	Implementation measures (Aim 1)							
Feasibility	extent to which AYA NA-	Feasibility of Intervention Measure	AYAs	Postintervention				
	SB can be successfully used (FIM) ²⁰			AYA survey				

	in cancer programs		Providers	Postintervention provider interview
Acceptability	perception of whether AYA-NA-SB is agreeable,	Acceptability of Intervention Measure (AIM) ²⁰	AYAs	Postintervention AYA survey
	palatable, or satisfactory to users		Providers	Postintervention provider interview
Appropriateness	SB's fit, relevance, or Measure (IAM) ²⁰		AYAs	Postintervention AYA survey
	compatibility with the context in which it will be used		Providers	Postintervention provider interviews
Fidelity	the degree to which AYA NA-SB is implemented as intended	Proportion of needs assessment reviewed by provider within one week and referral pathways initiated	Providers	Fidelity checklist
Implementation determinants	Perceived barriers and facilitators to AYA NS-SB implementation	Qualitative analysis of perceived determinants based on CFIR constructs	Providers	Postintervention provider interview
Implementation strategies	Strategies deployed to facilitate AYA NA-SB implementation	Qualitative analysis of strategies used and their perceived level of influence	Providers	Postintervention provider interview
	Service	e and patient outcomes (Aim 2)		
AYA needs	variables(?)	crosstab with demographic/clinical	AYAs	Needs assessment

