Appendix B: Fidelity checklist

Assessment ID					
(see top of assessment)					
Assessment Date (see timestamp at top of			/ /		
assessment)				-	
Date I reviewed assessment			//	_	
Date in which I initiated referral pathways			//	_	
Referral pathways initiated	Need # Referral Pathway				
For needs indicated by this	Completely	Disagree	Neither agree	Agraa	Completely
AYA, I was confident about	disagree	Disagree	nor disagree	Agree	agree
which referral pathways to initiate	0	2	3	4	S

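### The fidelity measure credits only initiated referral pathways, and the checklist cannot record a referral list, although a list is an equally intended action when the AYA prefers it

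*Combined protocol and SAP*

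**What the plan says.** The Fidelity row of the Outcome Measure(s) table defines the construct as "the degree to which AYA NA-SB is implemented as intended". The measure is "Proportion of needs assessment reviewed by provider within one week and referral pathways initiated", and the fidelity checklist is its only data source.

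The Referral pathway initiation paragraph, under Instruments & procedure (Aims 1,2), describes what is intended. Within seven calendar days of completion the implementation leader reviews the assessment and "will either (a) initiate appropriate referral pathways, or (b) provide a list of recommended referrals to AYAs". The AYA's "preferences indicated at the end of the needs assessment" decide which. The same paragraph says that the checklist "timestamps their completion of these tasks, documents the referral pathways selected".

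Appendix B holds an assessment ID, an assessment date, two action dates ("Date I reviewed assessment" and "Date in which I initiated referral pathways"), rows headed "Referral pathways initiated", and one confidence item. It has no field for a list and no date for one.

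The Analytical Plan for Aim 1 calls for descriptive statistics on the quantitative implementation outcomes. It sets no fidelity target and no rule for scoring the list option.

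**The concern.** The measure does not match its own definition. Delivery as intended includes giving a list to an AYA who asked for one, but the measure credits only initiated pathways. The AYA's choice, which says nothing about provider performance, can therefore lower the score.

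The form adds a second problem. The procedure promises a timestamp for the tasks and a record of the pathways *selected*. The form asks only for pathways *initiated*. A provider who gave a list could leave those fields blank or could enter the recommended referrals in them. The same conduct can then score as failure or as success.

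This matters because implementation outcomes are the main focus of the pilot, and fidelity is the only quantitative Aim 1 measure taken from recorded provider actions; the others are AYA ratings. If fidelity is included in the planned bivariate analyses, literal scoring would make a subgroup that more often prefers lists look less well served, even under perfect delivery.

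**Working it through.** The plan states no fidelity figure, so there is none to reproduce. The check compares procedure, measure and form, and then shows what the mismatch does to the proportion.

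**Inputs.** The planned sample is N = 25 to 50 AYAs (Sample Size); N is taken here as the number of completed assessments. The documents do not give the share preferring a list, so every count below other than N is an assumption. It is assumed that each AYA reports at least one need, and that preference is collected as the procedure says and can be linked by assessment ID.

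**Step 1: what the form can show for an AYA who prefers the list, with review on time.**

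| Provider's conduct | Initiation fields | Literal score |
|---|---|---|
| List given | blank | failure |
| List given | recommended referrals and date entered | success |
| No action | blank | failure |
| Pathways initiated instead | filled | success |

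Rows 1 and 3 look the same on the form, and so do rows 2 and 4. Linking preference shows what should have happened, not what did.

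**Step 2: literal scoring under perfect delivery.** Let m be the number who prefer the list. Fidelity is (N − m)/N, a loss of 1/N per AYA: 1/25 = 4 points, 1/50 = 2 points.

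| m (assumed) | N = 25 | N = 50 |
|---|---|---|
| 1 | 24/25 = 96% | 49/50 = 98% |
| 5 | 20/25 = 80% | 45/50 = 90% |
| 10 | 15/25 = 60% | 40/50 = 80% |

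The correct figure in every cell is 100%. At m = 0 there is no loss.

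**Step 3: what stays unresolved after linking preference.** Let x be the pathway-preferring AYAs handled on time, and k the list-preferring AYAs whose initiation fields are blank. Suppose that the other m − k list-preferring AYAs have an on-time date, accepted as evidence of action. Overall fidelity then lies between (x + m − k)/N and (x + m)/N, a width of k/N.

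Example (assumed): N = 25, m = 5, x = 18. Fidelity among pathway-preferring AYAs can be scored: 18/20 = 90%. Overall:

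- k = 5: 18/25 = 72% to 23/25 = 92%, width 5/25 = 20 points.
- k = 2: 21/25 = 84% to 23/25 = 92%, width 2/25 = 8 points.
- k = 0: 23/25 = 92%, width 0.

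At N = 50 with m = 10 and x = 36, fidelity among pathway-preferring AYAs is 36/40 = 90%. With k = 10, overall fidelity lies between 36/50 = 72% and 46/50 = 92%.

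The 72% to 92% range is the worst case, in which every list-preferring AYA's fields are blank.

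**The case against.** The best defence is that *initiated* is the protocol's name for the whole step. The paragraph heading and the timeline table both use that label, and no separate list step is shown. The paragraph also says that the leader documents these actions, meaning both. This is a fair reading, and it would remove the literal penalty. But in the operative sentence the verb belongs to option (a) only, set against (b), and shorthand does not give the form a place for a list or its date.

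Other mitigations help only in part. The implementation leader reviews the assessments and completes the checklists, and could apply one convention agreed at training, but none is written. The AYA survey in Appendix C offers educational materials and *other* as follow-up care, either of which might capture a list. Neither gives a date, and the survey is not a source for fidelity. One might also say that the one-week limit in the measure attaches only to review, which is always dated. The procedure, however, puts the seven days on both review and action.

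Two stronger readings are tempting but not supported. A reader might infer that a list can never be told from inaction. That holds only where the initiation fields are blank; a filled, dated entry points to action of some kind. A reader might also infer that the Aim 2 provider measure of services rendered will be miscounted. That table cell is broken in the available text, and entries for list-preferring AYAs could be flagged through linked preference.

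It also stands that this is a single-arm feasibility pilot with descriptive analysis, so no decision depends on the figure.

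**Conclusion.** The point holds with high confidence as a mismatch between procedure, measure and form. On the literal reading, each list correctly given costs 1/N. On the shorthand reading, the form still leaves overall fidelity unresolved by at most k/N, counting a filled, on-time date as evidence of action. Fidelity among pathway-preferring AYAs, and timely review for all, can still be scored.

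The total size is unknown, because it depends on how many AYAs prefer a list and how their forms are completed. It may be zero. A reader might take the 60% or 72% figures above as forecasts; they are illustrations from assumed counts.

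The conclusion also assumes that preference is collected. The item is not visible in the available text of Appendix A, which may be an extraction loss and is not held against the plan.

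The point is worth fixing before data collection, since the date of an unrecorded list may not be recoverable later.

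**What to change.** - **Measure.** Define fidelity, over all completed needs assessments, as review plus the preference-matched action (pathways initiated or list provided), both within seven calendar days of completion. Judge assessments that report no needs on timely review alone, since there is nothing to refer.
- **Form.** Add to Appendix B a field for the date on which the referral list was provided. The pathway rows then read as initiated or recommended according to which date is filled.
- **Reporting.** Give timely review and matched action separately, with counts by option (pathways, list, no needs).

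With these changes, perfect delivery scores N/N = 100% whatever the AYAs prefer. The cost is one reworded table cell, one extra date on a short checklist, and a few more lines in the report. The assessment ID and assessment date are already on the form, and the procedure already has preference indicated in the needs assessment. The change leaves the procedure as it is and only aligns the measure and the form with it.

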Aim 1/2: I will pilot AYA NA-SB in the North Carolina Cancer Hospital (NCCH). NCCH is a public, National Cancer Institute-designated Comprehensive Cancer Center located in central North Carolina, in a relatively metropolitan area. At NCCH, around 450 individuals ages 15-30 are diagnosed each year. About one third of these patients are treated in pediatric oncology and the remainder in adult oncology. NCCH's AYA program was established in 2015 with funding from a local nonprofit organization, the BeLoud Sophie Foundation. This funding was initially allocated towards hiring one fulltime employee (a social worker/program director) to provide AYA-specific care at NCCH. Since 2015, the program has evolved, hiring new AYA-specific staff members (e.g., nurse practitioner, fertility counselor) and expanding program activities and reach.

Aim 3: I will conduct interviews with providers and program leaders from AYA programs around the country.

Subjects selection criteria

• Inclusion Criteria

Aim 1/2: AYAs with cancer ages 18 through 39 currently in treatment at NCCH Aim 3: AYA providers and program leaders from around the country

• Exclusion Criteria

No exclusion criteria

• Sample Size

- Aim 1/2
 - \circ N=25-50 AYAs
 - o N=25/arm has been proposed as the minimum threshold of sample size for aims related to instrumentation. ¹⁸ Given that this is a single-arm pilot study, we have determined that a sample size between 25 and 50 is appropriate.
- Aim 3
 - N=8 AYA providers/ program leaders. Interviewees will be purposefully sampled such that
 they represent a range of health systems. As such, a sample size of 8 is expected to yield
 adequate data to meet the objectives of Aim 3.

Interventions and Interactions

Intervention (Aims 1, 2)

The intervention, AYA NA-SB, includes three components: (1) a needs assessment, (2) a map of referral pathways, and (3) implementation guidance (**Appendix A**).

Needs assessment. The needs assessment portion of AYA NA-SB is a 57-item PROM which includes nine domains: (1) information, (2) cancer care team, (3) physical health, (4) emotional health, (5) sexual and reproductive health, (6) health behaviors and wellness, (7) work and education, (8) peer support and programming, and (9) finances and everyday needs.

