Referral pathways. Each domain of the needs assessment triggers a specific referral pathway. For example, needs reported in the 'sexual and reproductive health' domain trigger a referral to a fertility counselor or specialist while needs reported in the 'work and education' domain trigger a social worker visit. NCCH will tailor the map of referral pathways to their institution prior to the onset of data collection such that AYAs' needs are triaged to the appropriate parties at their institution.

Implementation guidance. Based on data collected during AYA NA-SB development, we compiled a list of potential implementation barriers and implementation strategies hypothesized to mitigate them. Participating NCCH providers will be given this information to inform their own deployment of strategies. To enhance the real-world applicability of findings, the implementation strategies will not be explicitly prescribed to NCCH, but the strategies they use will be carefully documented to contextualize findings.

Instruments & procedure (Aims 1,2)

Provider training. Six weeks prior to the onset of data collection, participating NCCH providers will participate in a 3-hour group training to familiarize them with the intervention and pilot protocol. In addition to the implementation leader, additional relevant providers identified by the implementation leader will participate in this training.

During the first hour of the training, I will provide an overview of AYA NA-SB and its development as well as a detailed summary of the pilot protocol. During the second hour of the training, we will collaboratively identify appropriate referral pathway providers for each needs assessment domain, explicitly outlining the

processes needed to initiate these referral pathways. During the third hour, we will brainstorm potential implementation strategies that might be deployed to facilitate AYA NA-SB implementation.

Needs assessment administration. The needs assessment portion of AYA NA-SB will be administered to AYAs through a secure online survey platform, RedCAP, and will take approximately 15 minutes to complete. The survey link will be delivered to AYAs through a patient portal message from the implementation leader. AYAs will receive a \$15 incentive for completing the needs assessment.

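### Fidelity is one proportion per needs assessment, although the intervention works domain by domain and allows a referral list instead, so partial or off-map referral can pass and a correctly handled list can fail

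*Combined protocol and SAP*

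**What the plan says.** The Outcome Measure(s) table, under the Aim 1 implementation measures, defines fidelity as "the degree to which AYA NA-SB is implemented as intended". It measures it as "Proportion of needs assessment reviewed by provider within one week and referral pathways initiated", taken from the fidelity checklist.

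What is intended is set out under Interventions and Interactions:

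- The needs assessment is a "57-item PROM which includes nine domains".
- On referral: "Each domain of the needs assessment triggers a specific referral pathway". The hospital tailors the map of pathways before data collection starts.
- Under Referral pathway initiation: "Within seven calendar days of AYA NA-SB completion, the implementation leader will review completed needs assessments". The same sentence goes on to the action: depending on the AYA's stated preference, the leader "will either (a) initiate appropriate referral pathways, or (b) provide a list of recommended referrals to AYAs".

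Appendix B, the checklist, has a review date, a single field "Date in which I initiated referral pathways", rows headed "Need # Referral Pathway", and one item on how confident the leader was in choosing pathways. No field for the list option is visible. The Analytical Plan gives descriptive statistics for the implementation outcomes and sets no fidelity target.

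**The concern.** A fidelity measure should reproduce the intervention's own unit, actions and time limit. This one departs from all three.

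- **Unit.** Up to nine domains can trigger a pathway, but the assessment is scored once. No rule says whether some pathways are enough or all are needed, or whether they must match the map. The only check on choice is the leader's own confidence.
- **Action.** Giving the AYA a list is a permitted action, yet the measure credits only initiated pathways.
- **Time.** In the table cell the one-week limit attaches to review; in the procedure it opens a sentence covering review and action.

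Aim 1 focuses mainly on implementation outcomes. The rationale for the tool is that needs questionnaires fail when they are not linked to services. Fidelity is also what helps separate an intervention that was not delivered from one that was delivered and did not help. The pilot data are later discussed with other health systems in Aim 3, so an unclear figure would carry into scale-up planning.

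**Working it through.** The plan gives no fidelity figure, target or expected rate, so there is nothing to reproduce. The check is whether the same referrals give different fidelity under the readings that the cell allows.

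**Inputs from the documents:** 9 domains; one pathway per domain; 25 to 50 AYAs; two permitted actions; seven days.

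**Assumed, because the documents give neither:** m, the number of domains with a reported need per AYA; q, the chance that a triggered pathway is initiated.

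**1. Worked case, with no probability model.** Take 25 AYAs who prefer that pathways be initiated, four reported domains each, and one pathway opened for each AYA.

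- Any pathway suffices: 25/25 = 100%.
- By domain: 25/(25 × 4) = 25/100 = 25%.
- All pathways required: 0/25 = 0%.

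**2. General case, with domains independent.** Any = 1 − (1 − q)^m; by domain = q; all = q^m.

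For m = 4, q = 0.7: any = 1 − 0.3^4 = 99.2%; by domain 70%; all = 0.7^4 = 24.0%.

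| m | Any, q = 0.5 to 0.9 | By domain | All, q = 0.5 to 0.9 |
|---|---|---|---|
| 1 | 50% to 90% | 50% to 90% | 50% to 90% |
| 2 | 75% to 99% | 50% to 90% | 25% to 81% |
| 4 | 94% to 100% | 50% to 90% | 6% to 66% |
| 6 | 98% to 100% | 50% to 90% | 2% to 53% |

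With one reported domain the rules agree; they diverge as m grows.

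**3. Independence.** One leader handles the whole assessment, so pathways are probably positively correlated. At the extreme, all or none are opened in each assessment, and all three rules give q. For m = 4, q = 0.7, moving from independence to that extreme takes the any-pathway score from 99% to 70% and the all-pathways score from 24% to 70%. The independence figures are therefore the wide end of that range.

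**4. The opposite error.** Let s be the share of assessments in which the AYA chose the list. Read literally, these have no pathway initiated, so fidelity cannot exceed 1 − s however well the protocol was followed. For s = 0.10, 0.25 and 0.50 the ceiling is 90%, 75% and 50%. The documents do not give s. AYAs who report no need raise the same problem.

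**5. Can existing data support a domain-level score?** Mostly. Checklist rows carry a need number, Appendix A places each item in a domain, and the assessment ID links the two. Three things are missing: a date per pathway, a field for the list, and a rule for which responses (agree, somewhat agree, not sure) count as a reported need.

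**The case against.** The strongest reply is that the cell speaks of pathways in the plural and the procedure speaks of appropriate ones, so requiring all of them is at least as natural a reading. Missed referrals would then lower fidelity. This stands as far as it goes. A reader might infer that measured fidelity will approach 100% whatever is delivered; that holds only if any single pathway suffices, which the documents nowhere say. What remains is that the rule is unstated. If the cell is instead read as two proportions, the second has no stated denominator.

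A reader might also infer that late referral would go unnoticed. That is weak. The procedure's seven-day window covers action, the activity timeline puts initiation one week after administration, and Appendix B records an initiation date. A wholly late referral is detectable. What is left is that the cell attaches its limit to review and that one date per assessment cannot show a single late pathway.

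Finally, it can be said that failure would not be hidden, because Aim 2 reports needs, services rendered, care coordination and needs met, partly from the same checklist. That is fair and limits the harm. Those outcomes do not define fidelity, however, and the readable part of the services row compares nothing with the map. That row is incomplete in the text available, so little weight is placed on it.

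**Conclusion.** The point holds as a mismatch between the measure and the intervention it is meant to track. The measure does not separate complete from partial or off-map referral, attaches its time limit only to review, and can score a protocol-compliant list as a failure. The error can therefore run either way, and the documents do not support a claim that fidelity will be inflated.

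The scoring rule alone moves the result from 100% to 25% to 0% in the worked case, and from 99% to 70% to 24% at m = 4, q = 0.7 under independence. The domain counts, initiation rates, independence and list share are assumptions; these figures show how far the readings can diverge and do not estimate bias.

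The impact is moderate: this is a single-arm pilot of 25 to 50 AYAs, and fidelity is descriptive with no threshold. It should still be changed, because a descriptive proportion needs a defined numerator and denominator, and a measure closer to the intervention is available at little cost.

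**What to change.** Replace the Fidelity cell with three measures:

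1. **Review:** the proportion of all completed assessments reviewed within seven calendar days of completion.
2. **Domain-level fidelity:** the number of domains with a reported need for which the action matching the AYA's stated preference was documented within seven days of completion, divided by all domains with a reported need. The action is the mapped pathway initiated or, for AYAs who chose the list, the mapped referral included on it.
3. **Complete fidelity:** among assessments with at least one reported need, the proportion in which every such domain met measure 2.

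State in advance which item responses count as a reported need.

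In Appendix B, add a tick box for the list option and let the need and pathway rows also record what was listed. For timeliness, either use the existing assessment-level date, completed for the list as well, and say so, or add a date to each row.

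**Cost:** one reworded table cell, two small checklist edits, and a join of the checklist to the needs assessment and the tailored map by assessment ID and item number. No new instrument or participant contact is needed. Reported fidelity may be lower than under a lenient reading of the current cell, although crediting the list option works in the other direction.
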